## 2. LIST OF ABBREVIATIONS

Abbreviation	Definition
(e)CRF	(Electronic) Case Report Form
(S)AE	(Serious) Adverse Events
ANSM	French National Agency for Medicines and Health Products Safety
AP	Accelerated phase
BP	Blast phase
BCR-ABL	Breakpoint Cluster Region – Abelson
CCTIRS	Consultative Committee for Processing of Information in Field of Scientific research

CI	Confidence interval
CML	Chronic Myeloid Leukemia
CNIL	National Commission on Data Processing and Freedoms
CP	Chronic phase
CPP	Ethics Committee
CRA	Clinical Research Associate
ECOG	Eastern Cooperative Oncology Group
ELN	European Leukemia Net
EMA	European Medicines Agency
ENCEPP	European Network of Centres for Pharmacoepidemiology and Pharmacovigilance
FACT-leu	Functional Assessment of Cancer Therapy – Leukemia
FISH	Fluorescence In Situ Hybridization
FPFV	First Patient First Visit
GPP	Good Pharmacoepidemiologic Practice
GVP	Guidelines on good pharmacovigilance practices
ICN	Information and Consent Note
IFN<math>\alpha</math>	Interferon alpha
ISEP	International Society for Pharmacoepidemiology
LPLV	Last Patient Last Visit
MA	Marketing authorization
MCR-C/P/m	Major Cytological Response - Complete/Partial/Minor
MHR-C/P	Major Hematological Response - Complete/Partial
MMR-C/P	Major Molecular Response - Complete/Partial
NMC	National Medical Council
PASS	Post Authorization Safety Study
Ph-	Philadelphia chromosome negative
Ph+	Philadelphia chromosome positive
Ph1	Philadelphia chromosome
PHC	Public Health Code
PV	Pharmacovigilance
QC	Quality Control
RT-PCR	Reverse Transcriptase Polymerase Chain Reaction
SmPC	Summary of Product Characteristics
TKI	Tyrosine Kinase Inhibitor
WHO	World Health Organization
WMA	World Medical Association

#### 4. SYNOPSIS

Title	BOSEVAL: An observational study - Evaluation of efficacy and safety of Bosulif® under real life conditions of use
Identifier of protocol version	Version 2.0
Date	15-FEB-2019
RATIONALE:	In spite of recent advances in treatment and management of patients with chronic myeloid leukemia (CML), an important unmet medical need persists for many patients who are resistant or intolerant to one or more tyrosine kinase inhibitors (TKI). Treatment with bosutinib offers an additional alternative for patients with CML resistant or intolerant to one or more previous therapies with TKI. In light of the availability of several targeted therapies for treatment of CML, each of which has a specific safety and tolerability profile, it is important to evaluate the efficacy, safety and modalities for use of these treatments under real-life conditions in France. This non-interventional study will make it possible to obtain data under real-life conditions of use of bosutinib in treatment of CML (all phases combined) in patients previously treated with one or more TKI and for whom imatinib, dasatinib or nilotinib are not considered as appropriate treatments.
OBJECTIVES:	
Primary objectives:
 
 
- To determine the percentage of patients with chronic phase (CP) Ph+/- CML or blast phase CML presenting with AE considered related to bosutinib by the participating doctor.
 
- To evaluate the percentage of patients who permanently discontinued bosutinib after an AE considered related to bosutinib by the participating doctor.
 
 
Secondary objectives:

	
 
- To determine the safety profile of bosutinib.
 
- To evaluate adherence of patients to treatment with bosutinib.
 
- To evaluate quality of life of patients treated with bosutinib.
 
- To describe modalities of treatment with bosutinib under real life conditions of use.
 
- To evaluate the efficacy of treatment with bosutinib.
 
- To describe the hematological, cytogenetic and molecular responses.
 
- To describe the characteristics of patients treated with bosutinib.
 
- To evaluate cross intolerance between bosutinib and previously prescribed tyrosine kinase inhibitors.
 

Study Design	
Non-interventional observational multicentric prospective study not affecting the patient's medical care.

POPULATION CONCERNED:	
Criteria for inclusion:
 
 
• Male or female patient 18 years of age or older;
 
• Patient with Philadelphia chromosome positive or negative CML, or BCR-ABL positive, chronic, accelerated or blast phase;
 
• Patient resistant or intolerant to previous therapy with a TKI for CP, AP or BP CML other than bosutinib;
 
• Patient initiating bosutinib for treatment of CP, AP or BP Ph+/- CML, at the end of the inclusion visit or during the month preceding it;
 
• Patient who has been informed that a method of contraception must be used if a risk of pregnancy exists;
 
• Patient who has been informed about the study and who signed his or her consent form.
 
 
Criteria for non-inclusion:
 
 
• Patient with Philadelphia chromosome
 

	
negative CML, BCR-ABL negative chronic, accelerated or blast phase CML.
 
 
• Patient recently diagnosed with CML and who has not received previous treatment with TKI;
 
• Patient currently treated with a treatment other than bosutinib
 
• Patient of childbearing potential not using a method of contraception;
 
• Patient treated in the setting of an interventional study for another disease (outside of follow-up period);
 
• Patient who refuses computer processing of his/her medical data.
 


NATURE AND DURATION OF STUDY
	
This is a national, observational, descriptive, prospective, multi-centre study conducted in Metropolitan France in adult patients treated for chronic phase, accelerated or blast phase Philadelphia chromosome positive (Ph+/-) CML, previously treated with one or more TKIs and for whom imatinib, dasatinib or nilotinib are not considered as appropriate treatments. The study will be conducted in all centres involved in management of CML, i.e. about twenty (20) centres are expected.
 
The study will be offered to all patients who satisfy criteria for eligibility up to the end of the recruitment period. Eligible patients but not included in the study will be recorded in a non-inclusion registry.
 
Patients will be followed prospectively throughout the duration of the study (3-year follow-up) starting from their inclusion in the study. Follow-up data will be collected at follow-up visits conducted in the setting of usual management, estimated at every 3 months independently of discontinuations, changes or discontinuations of treatment possibly implemented. Therapeutic management of the patient will not be

	
changed by participation in the study.


ORIGIN AND NATURE OF DATA COLLECTED
	
Patients will undergo collection of medical data indirectly by name at inclusion and during follow-up. Data collection will involve the following information:
 
 
- Compliance with criteria for inclusion and non-inclusion
 
- Demographic characteristics (year of birth, gender, weight, height, ECOG performance status)
 
- Description of CML (date of diagnosis and phase of CML at time of diagnosis, tests performed for diagnosis)
 
- History of therapeutic management: Descriptions of previous treatments of CML (type, dose, dosage, duration; better response to previous treatment; reasons for change in lines of treatment; type and grade of AEs which resulted in change of the previous line of treatment, better response obtained)
 
- Characteristics of patients at time of initiation of treatment with bosutinib: comorbidities and previous conditions, performance status, concomitant treatments
 
- Biochemistry and hematological assessments (at time of inclusion and follow-up)
 
- Description of CML at time of initiation of bosutinib (phase at initiation, responses to treatments and types of tests performed)
 
- Description of initiation of treatment with bosutinib (date of initiation, dose, dosage)
 
- Description of changes to treatments (bosutinib: changes to dose or dosage, temporary or permanent discontinuation of treatment; change to concomitant treatments)
 
- Safety and tolerability and management of toxicities related to bosutinib (concomitant treatments, additional corrective medical measures)
 

	
 
- Hematological, cytogenetic and molecular tests performed for monitoring of response to treatment
 
- Compliance with treatment
 
- Quality of life
 

Number of patients	
Since CML is a rare disease, a minimum number of patients is not expected. Therefore, in this context about 100 patients included in the study appears to be a reasonable objective, which will make it possible to have acceptable precision for estimates measured.

DATA ANALYSIS	
All tests will be performed with a type 1 error <math>\alpha = 5\%</math>.
 
A descriptive analysis of qualitative and ordinal variables will consist of the sample size and frequency of each modality with its 95% confidence interval (CI). Quantitative variables will be described for the overall population and for each cohort (chronic phase, accelerated phase, blast phase) of patients analyzed, in terms of sample size, mean and medium, standard deviation (SD), confidence interval, as well as number of missing data.
 
An estimate of progression-free survival (PFS) and of overall survival (OS) will be measured by the Kaplan-Meier method. The survival function <math>S(t)</math> will be the probability that the event of interest (progression or death respectively) does not occur before date <math>t</math>. The percent survival will be estimated and described in each of the cohorts of interest.
 
Data will be evaluated separately for patients presenting with chronic phase, accelerated phase or blast phase Philadelphia chromosome +/- CML and depending on treatment line.
 
Interim analyses will be performed if necessary.

## 5. AMENDMENTS AND UPDATES

All substantial amendments to the protocol, including a brief description of the reason for each amendment, the dates of each of the changes and a reference to the section of the protocol targeted by the change are listed in the following table. The amendments are

numbered consecutively. Updates performed by PACL (Protocol Administrative Change Letter) will be described in the table if and when a substantial amendment then is added.

A substantial amendment is a change that may have an impact on the safety of use and physical or psychological well-being of participants in the study or which can affect results of the study and their interpretation, for example, changes to the primary or secondary objectives of the study, the study population, the study design, the source of the data, the method of collection of data, the sample size, definitions of principal exposure, results and confounding factors, as well as the analytical plan as described in the protocol.

Amendment number	Date	Section(s) of protocol changed	Summary of amendment(s)	Reason
1	22-JAN-2019	Liste 2. LIST OF ABBREVIATIONS  3. PARTIES RESPONSABLES  4. RÉSUMÉ  6. ÉVÉNEMENTS IMPORTANTS  9.1. Schéma de l'étude  9.2.1. Critères d'inclusion  9.4.1. Données patient  9.7. Analyse des données  9.8. Contrôle qualité  11. PRISE EN CHARGE ET NOTIFICATION DES ÉVÉNEMENTS INDÉSIRABLES / DES EFFETS INDÉSIRABLES	The amendment has been written in order to include Ph(-) patients in the analysis.  To specify criteria for inclusion in order to facilitate understanding by the investigators and the Clinical Research Associates.  The inclusion period has been extended by 24 months.  Update of the CRF and precision of data following on-site monitoring.  Update of all documents relating to the study following effective application of the GDPR law.  Update the AEM form.	

## 6. IMPORTANT EVENTS

**Table 1: Provisional schedule**

Important event	Planned date
Conduct of evaluation of feasibility	December 2014 – January 2015
Submission of the study to the CNOM (National Medical Council)	23-DEC-2014
Authorization of the CNIL	22-JUL-2015
Start of data collection	22-OCT-2015
End of data collection	DEC 2019
Recording in the EU PAS registry	November 2014
Study final report	DEC 2023

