### **9.1. Study design**

This is a national, observational, descriptive, prospective, multicentre study conducted in metropolitan France in adult patients treated for accelerated or blast phase Philadelphia chromosome positive chronic myeloid leukemia, previously treated with one or more TKIs and for whom imatinib, nilotinib and dasatinib are not considered as appropriate treatments. The study will be conducted in all centres involved in management of CML, i.e. about twenty (20) in expected centres.

[figure not shown]
The study will be offered to the totality of patients who satisfy criteria for inclusion and for non-inclusion up to the end of the inclusion period defined as 4 years. About one hundred

(100) patients included are expected in the study. Therapeutic management of a patient will not be changed by participation in the study and will depend on decisions taken by doctors in agreement with current international recommendations (European Leukemia Net, ELN network [13]) (see paragraph 7.3).

Patients will be followed prospectively over a 3-year period starting with their inclusion in the study. The inclusion visit will be performed at time of inclusion of the patient in the study, after which the patient has been informed and has accepted to participate by signing the consent form. Follow-up visits will be performed after usual consultation, estimated at about every 3 months. No visit or additional examination will be requested by the protocol: modalities for follow-up and treatment will be left up to the entire judgement of the participating doctor. Data will be recorded during the 3 years of the patient's participation, except in case of withdrawal of consent, death of a patient or termination of the study before its planned end.

Total duration of the study is estimated at 7 years with an inclusion period of 4 years and a follow-up period of 3 years (see Figure 1). Throughout the study, at least one monitoring visit per year will be performed.

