## **9.5. Study sample size**

Since the descriptive objective of this study does not involve the hypothesis of specific research, it is not necessary to calculate a minimum sample size population of participating

patients. Furthermore, since CML is a rare disease, a minimum number of patients is not expected.

Based on the number of monthly prescriptions of Bosulif® (sponsor data) and taking into account the future start-up of a competitive study, a total of one hundred (100) patients included in the study appears to be a reasonable objective. Participating doctors should include on average 5 patients in the study, with no distinction between phases of CML at inclusion.

However, it is shown that about one hundred patients would make it possible to have acceptable precision, precision corresponding to half of a 95% confidence interval (CI):

- $\leq 10\%$  to estimate a percent of patients presenting with a given event (Wald asymptotic method without a continuity correction – hypothesis of a 50% rate)
- Of 10% in order to estimate median survival (Greenwood formula under the hypothesis of absence of data censored at the right before median survival and occurrence of a single event at a time).

Consecutive inclusion of patients who satisfy eligibility criteria up to the end of the inclusion period estimated at 2 years will ensure the representativeness of patients in the study.

In order to ensure compliance with this consecutiveness, a registry of non-inclusion will be set up. Patients eligible but not included in the study must be recorded in this registry and throughout the period of inclusion. A minimum of parameters will be collected.

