### **9.7.1. Statistical methods**

#### **Description of data**

Patients' characteristics will be evaluated overall and then separately for patients with CP, AP or BP Ph+/- CML, and by line of treatment. Other data will be separately evaluated for patients presenting with CP, AP or BP Ph+/- CML and then by treatment line.

A descriptive analysis of qualitative and ordinal variables will consist of the sample size and the frequency of each modality with its 95% confidence interval (CI). Quantitative variables will be described in terms of sample size, mean and median, standard deviation, SD, confidence interval.

The description of variables collected during follow-up of each patient will contain a presentation of parameters for each of the times of measurement.

Overall survival data and progression-free survival (PFS) will be described with Kaplan Meier curves. Median survival will be estimated and presented with its 95% CI.

The sample size of missing values for each variable analysed will be indicated in the tables of results. Key data will be made obligatory in the electronic CRF in order to control the percent of missing data, if applicable, with models based on maximization of the function of probability or of techniques of attribution will be used.

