3.2 Does the protocol specify the primary and secondary (if applicable) endpoint(s) to be investigated?				
3.3 Does the protocol describe the measure(s) of effect? (e.g. relative risk, odds ratio, deaths per 1000 person-years, absolute risk, excess risk, incidence rate ratio, hazard ratio, number needed to harm (NNH) per year)				

Comments:

--

 Date from which the analytical dataset is completely available.

Section 4: Source and study populations	Yes	No	N/A	Page Number(s)
4.1 Is the source population described?				
4.2 Is the planned study population defined in terms of:				
4.2.1 Study time period?				
4.2.2 Age and sex?				
4.2.3 Country of origin?				
4.2.4 Disease/indication?				
4.2.5 Co-morbidity?				
4.2.6 Seasonality?				
4.3 Does the protocol define how the study population will be sampled from the source population? (e.g. event or inclusion/exclusion criteria)				

Comments:

--

Section 5: Exposure definition and measurement	Yes	No	N/A	Page Number(s)
5.1 Does the protocol describe how exposure is defined and measured? (e.g. operational details for defining and categorizing exposure)				
5.2 Does the protocol discuss the validity of exposure measurement? (e.g. precision, accuracy, prospective ascertainment, exposure information recorded before the outcome occurred, use of validation sub-study)				

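### The end of data collection in the section 6 schedule (DEC 2019) falls about 34 months before the last 36-month follow-up that section 9.1 requires; the 10% precision in section 9.5 is correctly calculated but attached to the wrong quantity

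*Protocol*

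**What the plan says.** **Schedule.** Table 1 in Protocol section 6 gives "Start of data collection 22-OCT-2015", "End of data collection DEC 2019" and "Study final report DEC 2023". Section 9.1 states: "Total duration of the study is estimated at 7 years with an inclusion period of 4 years and a follow-up period of 3 years". It also has each patient followed for three years from inclusion, and Table 4 schedules visits to M36.

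Section 9.5 gives a different inclusion period. It relies on consecutive inclusion "up to the end of the inclusion period estimated at 2 years will ensure the representativeness of patients in the study".

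The ENCePP checklist in Annex 2 lists end of data collection as a milestone and footnotes it as "Date from which the analytical dataset is completely available".

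**Precision.** Section 9.5 defines precision as half of a 95% confidence interval and gives two figures for about 100 patients. The first is at most 10% for a percentage (Wald, 50% rate). The second is 10% "in order to estimate median survival (Greenwood formula under the hypothesis of absence of data censored at the right before median survival", with events occurring one at a time. Section 9.7.1 then plans to report median survival with its own 95% interval.

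**The concern.** The end-of-collection date cannot be reached from the protocol's start date and durations. Such a milestone is used to plan site contracts, monitoring and database lock. Section 9.1 lets recording stop if the study is terminated before its planned end, so the planned end has to be unambiguous.

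Two sets of results would suffer if the date were followed. Progression-free and overall survival at 3 years are named secondary objectives (section 8.2). The second primary objective is the percentage of patients who stop bosutinib permanently after a related adverse event. Section 9.7.2 reports it as a plain percentage, so events after an early cut-off would simply not be counted.

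The second issue is smaller. A reader of section 9.5 would take it that median survival, which is a time, will be known to within 10%. The formula named there does not give that.

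**Working it through.** **1. Calendar**

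Inputs: start 22-OCT-2015 and end DEC 2019 (section 6, Table 1); inclusion 4 years and follow-up 3 years (section 9.1); inclusion 2 years (section 9.5).

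- Last inclusion: 22-OCT-2015 + 4 years = 22-OCT-2019.
- Last 36-month follow-up: 22-OCT-2019 + 3 years = 22-OCT-2022.
- Gap to the milestone: 33.7 months from 31-DEC-2019, or 34.7 months from 1-DEC-2019.
- With the 2-year inclusion of section 9.5: 22-OCT-2015 + 2 + 3 years = 22-OCT-2020, still 9.7 months after 31-DEC-2019.
- Start to 31-DEC-2019 is 50.3 months. That is the 48-month inclusion period plus 2.3 months, not the 84-month study.
- Final report: 31-DEC-2023 is 14.3 months after 22-OCT-2022, but 48 months after 31-DEC-2019.

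**2. What a DEC 2019 stop would leave**

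Assumption, not given in the protocol: uniform inclusion over 48 months. The figures are calendar limits only and ignore deaths and withdrawals. With a stop at 50.3 months, the share of patients who could reach follow-up time t is (50.3 − t)/48.

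| Follow-up | Calculation | Share |
|---|---|---|
| 12 months | 38.3/48 | 80% |
| 24 months | 26.3/48 | 55% |
| 36 months | 14.3/48 | 30% |

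Patients included after DEC 2016 could not reach 36 months. Mean available follow-up, capped at 36 months, is 0.298 × 36 + 0.702 × (36 + 2.3)/2 = about 24 months.

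**3. The 10% figures in section 9.5**

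Both reproduce from their stated inputs.

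- Percentage (Wald): 1.96 × √(0.5 × 0.5/100) = 0.098.
- Greenwood: SE = S × √Σ[d/(r(r − d))]. For the first 50 single events among 100 uncensored patients, the sum is Σ 1/(r(r − 1)) for r = 100 down to 51, which telescopes to 1/50 − 1/100 = 0.01. SE = 0.5 × √0.01 = 0.050, and 1.96 × 0.050 = 0.098.

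The result is 9.8 percentage points on the survival probability at the point where it equals 0.50.

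**4. What that means for the median as a time**

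The half-width on the time scale is the half-width on the probability scale divided by the event density at the median. For a Weibull curve with shape k, the relative half-width is 0.098/(0.5 × k × ln 2). The protocol gives no survival shape, so k is an assumption and a range is shown.

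| Shape k | Relative half-width of the median |
|---|---|
| 0.7 | 40% |
| 1 (exponential) | 28% |
| 1.5 | 19% |
| 2 | 14% |

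No value in this range gives 10%.

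**The case against.** **On the schedule.** The table is headed as provisional. Section 9.1 says data are recorded for each patient's three years, and Table 4 runs to M36; those passages govern conduct. The DEC 2023 report date supports the 7-year design, so DEC 2019 may be the end of inclusion entered in the wrong row. The Annex 2 footnote belongs to an unfilled checklist template. This makes an actual stop in DEC 2019 unlikely, and the 30% describes a scenario rather than a forecast. It does not remove the contradiction, which lies in current text and does not depend on the footnote. The amendment log records a 24-month extension of inclusion, which explains the 2 years in section 9.5 but does not make it consistent with section 9.1.

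A reader might infer that 3-year survival would come from the earliest patients alone. That goes too far: Kaplan-Meier estimation uses later patients until they are censored. The loss is one of precision at 3 years.

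**On precision.** A reader might infer that the 10% is miscalculated or hides its censoring assumption. Neither is so: it reproduces, and section 9.5 states the assumption in the same sentence. What remains is that the figure is placed on the wrong scale.

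A reader might also hold the 10% against the phase and treatment-line cohorts, because section 9.7.1 says "Other data will be separately evaluated for patients presenting with CP, AP or BP Ph+/- CML and then by treatment line". Section 9.5 claims no precision by cohort, and section 9.7.2 describes both primary percentages overall. The protocol predicts no phase split either, so half-widths by phase would have to borrow another study's case mix. Nor are survival probabilities at 1, 2 and 3 years missing: sections 8.2 and 9.7.3 already specify them.

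**Conclusion.** The schedule point stands and needs correction. DEC 2019 is about 34 months too early for the 4 + 3 year design and about 10 months too early even for the outdated 2-year inclusion period. This rests only on the protocol's own dates. That DEC 2019 was meant as the end of inclusion is a plausible inference, not something the protocol says. The consequence (about 30% of patients able to reach 3 years, mean available follow-up about 24 months instead of 36) holds only if the milestone is followed and inclusion is uniform.

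The precision point is a secondary wording correction. The 9.8 points are right for a percentage near 50%, or for a survival probability near 0.5, in all 100 patients without earlier censoring. They are not the precision of median survival time. Its relative half-width would be about 28% under an assumed exponential shape, and about 14% to 40% for Weibull shapes 2 to 0.7.

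**What to change.** 1. Reconcile sections 6, 9.1 and 9.5. In the section 6 schedule, set the end of data collection after the last patient's M36 visit, not before OCT 2022 on the 4-year inclusion. If DEC 2019 was meant as the end of inclusion, keep it in a separate row labelled so.
2. In section 9.5, change the inclusion period from 2 to 4 years.
3. In section 9.5, restate the precision as ±9.8 points for a percentage or a fixed-time survival probability in all 100 patients with no prior censoring, and delete the claim about median survival.

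The cost is one table row, one number and one sentence. No patients, visits or analyses are added. The stated precision becomes less favourable only in that it no longer covers the median.
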